11.2.7. Safety Analyses

Treatment-emergent AEs are defined as AEs occurring after the first dose of study drug through Day 8 in Part 1 (Day 16 in cohort 1C) and Day 21 (Day 12 in Cohorts 2D and 2E) in Part 2. Duration of treatment will be summarized by treatment group.

The incidence of all reported AEs and treatment-related AEs will be tabulated by treatment group. Adverse events will be classified by system organ class and preferred term using the Medical Dictionary for Regulatory Activities (MedDRA).

Adverse events will be listed and summarized by treatment group, MedDRA preferred term, severity, seriousness, and relationship to study drug. In the event of multiple occurrences of the same AE with the same preferred term in one participant, the AE will be counted once as the worst occurrence. The incidence of AEs will be tabulated by system organ class and treatment group. AEs leading to premature discontinuation of study drug or withdrawal from the study will be summarized and listed in the same manner.

Summary statistics for actual values and for change from baseline will be summarized for laboratory results by treatment group and scheduled visit. Participants with laboratory values outside of the normal reference range at any postbaseline assessment will be identified.

Data to be listed by subject and summarized by treatment will include AEs, vital signs, ECG parameters, and clinical laboratory evaluations. All values outside the clinical reference ranges will be flagged on the data listings. Other data to be listed by subject will include physical examination findings and concomitant medications.

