- 6 Only for women of postmenopausal status.
- 7 Serology screening will include tests for hepatitis B surface antigen, hepatitis C virus, and human immunodeficiency virus.
- 8 Standard clinical safety labs will be collected non-fasted.
- 9 PK samples to be collected before dosing (within 30 minutes) and at 0.25, 0.5, 0.75, 1, 1.5, 2, 2.5, 3, 3.5, 4, 6, 8, 12, 24, 36, and 48 h after dosing. Additional samples to be collected at 72 and 96 hours postdose for Cohorts 1C and 1D. Sampling windows are \pm 5 minutes for samples through 4 h postdose, \pm 10 minutes for samples at 6 and 8 h, \pm 30 minutes for samples from 12 to 48 h, and \pm 4 h for samples at 72 and 96 h. When ECGs and vital signs are scheduled at the same time as PK samples, the sample will be taken at the scheduled time point, with the ECGs and vital signs obtained as close as possible prior to the blood draw.
- 10 End of study visit for all cohorts except for the food-effect cohort, Cohort 1C. See Section 2.2 for schedule of events for days 8-16 for Cohort 1C.
- 11 Alcohol breath testing may be replaced with a question asking that participants confirm that they have refrained from any alcohol intake for the time period outlined in the protocol

2.2. Part 1 Cohort 1C Schedule of Events – Period 2

	Clinical Unit						EOS Visit ⁹
	Day 8	Day 9			Day 10	Day 11	Day 16
Assessments		Pre-dose	Dosing	Post-dose			(+/-1 d)
Unit Check-in	X						
Informed consent							
Inclusion/exclusion criteria	X	X					
Demographic data							
Medical history							
Prior medication history							
Vein assessment							
Physical examination ¹	X			X (abbrev)		X (abbrev)	X (abbrev)
Height							
Weight	X						
12-lead ECG ²	X	X		X	X	X	X
Vital signs ³	X	X		X	X	X	X
High-fat breakfast ⁴		X					
Study Drug			X				
Adverse event reporting ⁵	X	X	X	X	X	X	X
Concomitant medications	X	X			X	X	X
Alcohol breath test ¹⁰	X						
Drugs of abuse screen	X						
Pregnancy screen ⁶	X						X
Clinical Safety Labs ⁷	X			X	X		X
Plasma CC-42344 levels ⁸		X		X	X	X	
Discharge from Unit						X	

Footnotes

Note: The washout window between Period 1 and Period 2 may be optionally extended for up to 3 days, with other Period 2 visits adjusted accordingly. Thus, dosing for Period 2 may occur between Day 9 and Day 12.

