6. INVESTIGATIONAL PLAN

6.1. Summary of Study Design

This is a single-center, randomized, double-blind, placebo-controlled phase 1 study of the influenza A virus replication inhibitor CC-42344 given orally to healthy participants at a single site in Australia. Participants will be recruited by Linear Clinical Research Ltd. Screening assessments must be done to determine participant eligibility. Written consent must be obtained before conducting any study procedures.

Part 1: Single-Ascending Dose

Participants will be randomly assigned within each cohort to receive a single dose of CC-42344 or placebo. Doses will escalate in sequential dose cohorts. It is planned that 4 cohorts will be dosed with 8 healthy participants per cohort (6 active and 2 placebo in each cohort). Each cohort in Part 1 will include the initial dosing of a sentinel group (1 CC-42344 and 1 placebo) at least 24 hours before dosing the remaining 6 subjects in the cohort (5 CC-42344 and 1 placebo). The remainder of the cohort will only be dosed if, in the opinion of the investigator, there is no significant safety concern identified in the sentinel subjects within the first 24 hours after administration of the dose (CC-42344 or placebo). The following regimens are planned:

- Cohort 1A (N=8): 100 mg CC-42344 or placebo.
- Cohort 1B (N=8): 200 mg CC-42344 or placebo.
- Cohort 1C (N=8): 400 mg CC-42344 or placebo on Days 1 and 9 (food effect).
- Cohort 1D (N=8): 800 mg CC-42344 or placebo.

Cohort 1C will be a two-period sequential food-effect cohort in which participants will receive a single dose of study drug under fasted conditions on Day 1 and a single dose of study drug under fed conditions on Day 9.

After the study was conducted, it was found that the Cohort 1C PK data were not interpretable due to issues with the execution of the assay for plasma CC 42344 levels at the contracted laboratory. Therefore, an additional cohort (Cohort 1C-2) will be enrolled to generate the 400 mg PK and food-effect data. This cohort will comprise 6 participants, all of whom will receive a single 400-mg dose of open-label CC-42344 on Day 1 under fasted conditions and a single 400-mg dose of open-label CC-42344 on Day 9 under fed conditions. The study entry criteria, activities, and assessments will be the same as those described for the main study.

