9.3.2. Reporting Procedures for All Adverse Events

Investigators are responsible for monitoring the safety of participants who have entered this study and noting any event that seems unusual, even if this event may be considered an unanticipated benefit to the participant. The investigator is responsible for appropriate medical care of participants during the study.

The investigator remains responsible for following, through an appropriate health care option, adverse events that are serious or that caused the participant to discontinue the study. The participant should be followed until the event is resolved or explained. Frequency and method of follow-up are left to the discretion of the investigator and site policy.

Adverse event information will be collected through Day 8 (Part 1), Day 16 (Cohort 1C), and Day 21 (Part 2). Participants who discontinue study drug at any time will have adverse events collected through the planned end of study visit, *provided consent to continue in the study has not been withdrawn*.

The investigator is responsible for assessing and recording all adverse experiences. Each AE will be recorded and classified for intensity, seriousness, and causality. All AEs either observed by the investigator or reported by the participant will be recorded regardless of causality. The investigator will follow the participant until an AE resolves or stabilizes.

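### The treatment-emergent AE window ends on fixed nominal days: it does not move with the permitted shift of the fed dose, and it does not name Cohort 1C-2

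*Combined protocol and SAP*

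**What the plan says.** - **TEAE definition (Section 11.2.7).** The Part 1 rule covers "AEs occurring after the first dose of study drug through Day 8 in Part 1 (Day 16 in cohort 1C"). The Part 2 rule is "Day 21 (Day 12 in Cohorts 2D and 2E) in Part 2".
- **Use of the definition (Section 5).** TEAE incidence is the first-listed primary endpoint in both parts.
- **Permitted shift (note to the Section 2.2 schedule).** "The washout window between Period 1 and Period 2 may be optionally extended for up to 3 days, with other Period 2 visits adjusted accordingly". The note continues: "Thus, dosing for Period 2 may occur between Day 9 and Day 12".
- **Cohort 1C-2 (Section 6.1).** "This cohort will comprise 6 participants, all of whom will receive" active drug, including "a single 400-mg dose of open-label CC-42344 on Day 9 under fed conditions". Section 11.2.1 includes this cohort in the safety analysis.
- **AE collection (Section 9.3.2).** "Adverse event information will be collected through Day 8 (Part 1), Day 16 (Cohort 1C), and Day 21 (Part 2"). The AE footnote to the Section 2.2 schedule also gives Day 16.
- **End-of-study visits (Sections 2.1 to 2.4).** Each has a window of one day either side.

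**The concern.** The cut-offs are written as calendar days for named cohorts. They work only if every participant is dosed on the nominal day and every cohort is listed. The protocol departs from both conditions. A fed dose may be given up to three days late while the TEAE window stays where it was, and a cohort with a second dose on Day 9 has no entry of its own.

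A programmer who follows Section 11.2.7 exactly would drop AEs with late onset after the fed 400 mg dose from a primary endpoint. A programmer who departs from it would be choosing the window after the data exist, partly in an open-label cohort. Neither is desirable, and the definition can be settled now.

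**Working it through.** **Inputs.** Last dose days come from Sections 2 and 8.3.1 (Tables 1 and 2), cut-offs from Section 11.2.7, the permitted shift from Section 2.2, and cohort sizes from Section 6.1.

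**Step 1: reproduce the plan's cut-offs.** The protocol states no rule, but nominal last dose day + 7 gives every figure:

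- Cohorts 1A, 1B, 1D: 1 + 7 = Day 8.
- Cohort 1C: 9 + 7 = Day 16.
- Cohorts 2A to 2C: 14 + 7 = Day 21.
- Cohorts 2D, 2E: 5 + 7 = Day 12.

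Day 16 is therefore correct for Cohort 1C only when the fed dose is on Day 9.

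**Step 2: apply the permitted shift in Cohort 1C.** End of study = fed dose day + 7. Days covered = 16 − fed dose day. Days outside = end of study − 16. Share outside = days outside / 7.

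| Fed dose | End of study | Days covered | Days outside | Share outside | Days outside if the visit is on its +1 day |
|---|---|---|---|---|---|
| Day 9 | Day 16 | 7 | 0 | 0% | 1 |
| Day 10 | Day 17 | 6 | 1 | 14% | 2 |
| Day 11 | Day 18 | 5 | 2 | 29% | 3 |
| Day 12 | Day 19 | 4 | 3 | 43% | 4 |

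**Step 3: Cohort 1C-2.**

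- *Literal reading.* It is a Part 1 cohort outside the exception, so Day 8 applies. The fed dose is on Day 9, one day after the window closes, and 0 of 7 follow-up days are covered. This concerns 6 of the 12 planned active fed-dose participants (6 in 1C, 6 in 1C-2).
- *Probable intent.* Day 16 applies, all 7 days are covered for a Day 9 dose, and any extension brings back the losses in Step 2.

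**Step 4: visit window in all cohorts.** An end-of-study visit on its +1 day falls on Day 9, 17, 22 or 13, against cut-offs of Day 8, 16, 21 and 12. An AE with onset on that one day is outside the window.

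**Step 5: Part 2 collection days.** Section 9.3.2 gives Day 21 for all of Part 2. Sections 2.4 and 11.2.7 give Day 12 for Cohorts 2D and 2E. The difference is 21 − 12 = 9 days.

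**The case against.** The strongest reply is that this is a labelling gap with little effect. Several parts of it stand.

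- **Cohort 1C-2.** A reader might infer that all AEs after the fed dose in this cohort are lost. The documents do not support that as the intended rule. Section 6.1 says the cohort follows the main study's procedures, and Section 7.2.3 says its safety data will be analysed. The Period 2 schedule (Section 2.2) and the fed-dosing instruction (Section 8.4) are also headed Cohort 1C alone, yet must govern 1C-2. What remains is that Section 11.2.7 does not say so, while it does carry a separate entry for 2D and 2E.
- **Laboratory, vital-sign and ECG results.** A reader might infer that the final assessments are lost too. They are not. Section 5 lists them as separate endpoints, and Section 11.2.7 gives them no day limit.
- **Other AE tables.** Section 11.2.7 also tabulates all reported and all treatment-related AEs, so late events need not disappear from the report. This helps only if they were collected, and Section 9.3.2 states the same fixed Part 1 days for collection.
- **Late visits.** The definition depends on when an AE occurs. A symptom that began earlier but was reported at a late visit still counts.
- **Part 2 mismatch.** The longer period in Section 9.3.2 removes nothing from the TEAE count. It is an inconsistency only.
- **Decisions.** Escalation rests on the Safety Monitoring Committee's review of data up to 48 hours after dosing (Section 9.4), not on the TEAE window.

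It can also be said that Day 16 is only the name of an end-of-study visit that moves with the dose. That is a fair reading of the Section 2.2 footnote. Sections 9.3.2 and 11.2.7, however, state a day and refer to no visit, so the conflict with the permitted extension is not resolved.

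**Conclusion.** The point holds at moderate severity. The conflict between the fixed Day 16 cut-off and the permitted Day 9 to Day 12 fed dose needs no strained reading, and no other section cures it. Its size is 0 to 3 of 7 follow-up days (0 to 43%) per Cohort 1C participant, or 1 to 4 days if the end-of-study visit is on its +1 day. These figures assume that the end-of-study visit stays 7 days after the fed dose, as the nominal schedule implies.

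The Cohort 1C-2 gap is an ambiguity. It is total on the literal reading and nil on the probable intent with a Day 9 dose.

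A reader might infer a material downward bias in TEAE incidence. The rule can only lower the count, but the documents give neither the number of extensions nor any event timing, so no bias can be estimated. In Cohort 1C the cut-off also applies to active and placebo participants alike. For scale only: with 6 active participants, one whose sole TEAE is dropped changes the incidence by 1/6, or about 17 percentage points.

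**What to change.** - **Section 11.2.7.** Define TEAEs as AEs with onset or worsening after the first dose through the participant's actual end-of-study visit, including the visit window and any washout shift.
- **Cohort 1C-2.** Name it together with Cohort 1C in Section 2.1 (footnote 10), Section 9.3.2 and Section 11.2.7.
- **AE collection.** State the Part 1 limits in Section 9.3.2 and in the Section 2.2 AE footnote in the same visit-based terms, so that collection and analysis agree.
- **Part 2.** Reconcile the Day 21 limit in Section 9.3.2 with Day 12 for Cohorts 2D and 2E in Sections 2.4 and 11.2.7.
- **Reporting.** State how many Period 2 doses were given after Day 9.

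The cost is wording only. No visit is added, because the end-of-study visits already move with the dose.

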11.2.8. Interim Analyses

As described in Section 9.4, before dose escalation in the single-ascending dose and multiple-ascending dose cohorts, an SMC will review safety and available PK data to determine whether dose escalation may proceed.

12. ADMINISTRATIVE, ETHICAL, AND REGULATORY CONSIDERATIONS

The investigator is responsible for presenting the risks and benefits of study participation to the participant in simple terms using the informed consent document. The investigator will ensure that written informed consent is obtained from each participant by obtaining the appropriate signatures and dates on the informed consent document before the performance of protocol evaluations or procedures.

12.1. Ethical Review

The investigator will obtain documentation of the EC approval of the protocol and the informed consent document before the study may begin at the investigative site(s). The name and address of the reviewing EC are provided in the investigator file.

The sponsor will supply the following to the investigative site for submission to the EC:

- Protocol and amendments.
- Informed consent document and updates.
- Relevant curricula vitae, if required.
- Required safety and SAE reports.
- Any additional submissions required by the site's EC.

The investigator must provide the following documentation to the sponsor or its designee:

- The EC periodic (e.g., quarterly, annual) reapproval of the protocol.
- The EC approvals of any amendments to the protocol or revisions to the informed consent document.
- The EC receipt of safety and SAE reports, as appropriate.

12.2. Regulatory Considerations

This study will be conducted in accordance with the protocol and ethical principles stated in the 2013 version of the Declaration of Helsinki or the applicable guidelines on Good Clinical Practice, and all applicable federal, state, and local laws, rules, and regulations.

After reading the protocol, the investigator will sign the protocol signature page and return it to the sponsor or designee.

12.2.1. Investigator Information

The contact information and qualifications of the principal investigator and subinvestigators, and name and address of the research facility are included in the investigator file.

12.2.2. Protocol Amendments and Study Termination

The sponsor will initiate changes to the protocol as necessary (except for changes to eliminate an immediate hazard to a study participant) and seek approval by the EC before implementing. The investigator is responsible for enrolling participants who have met protocol eligibility criteria. Protocol violations must be reported to the local EC in accordance with EC policies.

The sponsor may terminate the study at any time. The EC must be advised in writing of study completion or early termination.

12.2.3. Study Documentation, Privacy, and Records Retention

All records connected with this clinical study will be retained for at least 2 years following the date of an approved marketing application or at least 3 years from the formal discontinuation of CC-42344 development; or 7 years from the end of the study, whichever is longer. All local laws regarding retention of records must also be followed. The study site is required to retain all records until written notification allowing destruction is received from Cocrystal Pharma Australia Pty Ltd.

To protect the safety of participants in the study and to ensure accurate, complete, and reliable data, the investigator will keep records of laboratory tests, clinical notes, and participant medical records in the participant files as original source documents for the study. If requested, the investigator will provide the applicable regulatory agencies and applicable EC with direct access to original source documents.

Records containing participant medical information must be handled in accordance with the requirements of the Health Insurance Portability and Accountability Act (HIPAA) Privacy Rule or equivalent (e.g., Privacy Act of 1988) and consistent with the terms of the participant authorization contained in the informed consent document for the study. Care should be taken to ensure that such records are not shared with any person or for any purpose not contemplated by the informed consent document. Furthermore, CRFs and other documents should be completed in strict accordance with the instructions provided by the sponsor, including the instructions regarding the coding of participant identities.

12.3. Study Finances

This study is financed by Cocrystal Pharma Australia Pty Ltd.

12.4. Publications

Cocrystal Pharma Australia Pty Ltd. Assures that the key design elements of this protocol will be posted in a publicly accessible registry. Neither the complete nor any part of the results of the study carried out under this protocol, nor any of the information provided by the sponsor for the purposes of performing the study, will be published or passed on to any third party without the consent of the study sponsor. Any investigator involved with this study is

obligated to provide the sponsor with complete test results and all data derived from the study.

14. DOCUMENT HISTORY

Document Version	Date
Version 5.0	17-Dec-2022
Version 4.0	12-Dec-2022
Version 3.0	18-Jun-2022
Version 2.0	17-Jan-2022
Version 1.1	21-Sep-2021
Version 1.0	26-Aug-2021

14.1. Summary of Changes from Version 4.0 to Version 5.0

Section	Change	Rationale
6.1 Summary of Study Design Synopsis Table 2	Added Cohorts 2D and 2E to the multiple-ascending dose (MAD) portion of the study.	Obtain safety and PK data for 400 mg QD and BID dosing of CC-42344 for 5 days to explore additional dosing regimens.
2 Schedule of Events	Added Section 2.4 to define the schedule of events for Cohorts 2D and 2E.	Added additional schedule of events to accommodate the shorter length of treatment for MAD cohorts 2D and 2E (5 days versus 14 days in the initial MAD cohorts). The general scheme for assessments is the same.
6.2 Dose Rationale	Added text supporting 400 mg QD and BID dose regimens.	Provide rationale for additional MAD cohorts (2D and 2E).
8.4 Dosage Administration	Added instructions for BID dosing.	Provide required operational information.
11.2 Statistical and Analytical Plans	Edited to reflect the additional cohorts to be included in the analyses.	Clarity and consistency.

14.2. Summary of Changes from Version 3.0 to Version 4.0

Section	Change	Rationale
6.1 Summary of Study Design Synopsis	Added Cohort 1C-2, an additional cohort to generate replacement 400 mg PK and food-effect data. Six participants will be treated with CC-42344 in a 2-period food design.	Obtain required PK data.
7.2.3 Participant Replacement 11.2 Statistical and Analytical Plans	Stated that the Cohort 1C-2 participants' PK data will replace the uninterpretable PK data from Cohort 1C, however the safety data from both cohorts will be included in the analyses.	Define plans for use of data from additional participants; confirm that safety analyses will include all participants treated with CC-42344.
8.5 Blinding and Unblinding	Noted that CC-42344 will be administered in an open-label manner in Cohort 1C-2.	Specify that treatment assignment will not be blinded in the additional cohort.

14.3. Summary of Changes from Version 2.0 to Version 3.0

Section	Change	Rationale
2 Schedule of Events	Optional replacement of alcohol breath testing with a question confirming abstinence	Mitigate risk of COVID-19 in the study clinic, as initially specified in Protocol Clarification Letter 3, dated 21-Feb-22
2 Schedule of Events	Add 72- and 96- hour postdose PK sample for Cohorts 1C and 1D	Better define the terminal elimination half-life, as initially specified in Protocol Clarification Letter 4, dated 24-Mar-22
2.2 Part 1 Cohort 1C Schedule of Events – Period 2	Allow optional extension of washout period between fasted and fed periods in Cohort 1C	Provide operational flexibility, as initially specified in Protocol Clarification Letter 2, dated 04-Feb-22
2.3 Part 2: Multiple-Ascending Dose Schedule of Events	Added specific PK sampling timepoints for Part 2	Provide PK data to support analysis of the multidose PK profile
6.1 Summary of Study Design (and Synopsis)	Changed the planned dose cohorts for the multiple-ascending dose part of the study (Part 2) from 200, 400, and 600 mg QD to 50, 100, and 200 mg QD	Favorable safety profile in Part 1, with PK data supporting predicted trough concentrations above the EC ₉₀ at the 50-mg QD dose level
6.2 Discussion of Design	Added text regarding the safety of the dose levels planned for Part 2 of the study	Provide rationale for dosing regimens for the multiple-ascending dose cohorts
7.1.2 Exclusion Criteria (and Synopsis)	Criterion 2: Change the allowable length of time between COVID-19 vaccination and randomization from 2 weeks to 7 days and expand the exclusion to cover all vaccines	Relax the COVID-19 vaccination timeframe, as initially specified in Protocol Clarification Letter 3, dated 21-Feb-22; include all vaccines for consistency
8.3.1 Formulation, Packaging, and Labeling	Adjust the number of capsules per dose in Part 2 to match the planned dose levels	Consistency with updated dose levels
8.4 Dosage Administration	Added instructions for a standardized breakfast prior to dosing	Specify controlled predose food intake
General	Editorial, formatting, and/or administrative corrections	Accuracy and consistency

